8.4.2 Secondary Endpoint

The secondary endpoint is the improvement in quality of life (QOL) of subjects after the ablation procedure. This endpoint will be measured by comparing the Atrial Fibrillation Effect on Quality-of-Life (AFEQT™) scores of subjects before and 12 months after the procedure.

The AFEQT™ includes 20 questions on a 7-point Likert scale. Questions 1-18 evaluate Health Related Quality of Life (HRQoL) and questions 19-20 relate to patients' satisfaction with treatment. The first 18 questions are used to calculate the overall AFEQT score and the subscale scores across three domains as follows:

- AF related Symptoms: Four questions (1 – 4)
- Daily Activities: Eight questions (5 – 12)
- Treatment Concerns: Six questions (13 – 18)

Overall and subscale scores range from 0 to 100. A score of 0 corresponds to complete disability, while a score of 100 corresponds to no disability.

Overall AFEQT scores assessed at baseline and at 12 months post procedure will be compared to see if QOL improved after treatment by testing the following hypothesis:

$$H_0: \mu_d \leq 0 \quad vs \quad H_A: \mu_d > 0 ,$$

where μ_d is the average change of the overall AFEQT scores between baseline and 12-month follow-up ($AFEQT_{12M} - AFEQT_{Baseline}$).

8.4.3 Additional Endpoints

No formal hypothesis testing will be performed for additional endpoints.

8.4.3.1. Additional Safety Endpoints

- Incidence of Unanticipated Adverse Device Effects (UADEs).
- Incidence of Serious Adverse Events (SAEs) within 7 days (early-onset), >7 to 30 days (peri-procedural), and >30 days (late onset) of initial ablation/repeat procedure, separately for each timeframe. SAEs that are deemed PAEs will be reported separately and will not be reported as part of the SAE estimates.
- Incidence of bleeding complication (ISTH definitions): a) major bleeding, b) clinically relevant non-major bleeding and c) minor bleeding.

The definition of SAEs can be found in section 14.2.2 of the study protocol. The ISTH bleeding complications definitions can be found in Appendix III (Study Definitions) of the study protocol.

8.4.3.2. Additional Effectiveness Endpoints

- **Acute procedural success:** Defined as the achievement of electrical isolation in all clinically relevant targeted PVs as evidenced by the confirmation of entrance block at the end of the index procedure. Use of a non-study catheter to achieve pulmonary vein isolation (PVI) due to an IRE-system malfunction is considered an acute procedural failure.
- **Acute reconnection:** Defined as the restoration of electrical conduction in any clinically relevant targeted PV as identified by adenosine/isoproterenol challenge during the index procedure.
- **First pass isolation (FPI):** Defined as the achievement of entrance block in all clinically relevant targeted PVs after first encirclement, evaluated prior to the adenosine challenge during the index procedure.
- **Touch-up by NSC:** Defined as the use of a NSC to achieve PVI in any clinically relevant targeted PV during the index procedure.

- **Repeat ablation procedures** for AF/AT/AFL of unknown origin during the 12-month follow-up period will be assessed. The evaluation will include the timing of repeat ablation (blanking period or evaluation period), any reconnections of PVs previously isolated during the index procedure, and the type of arrhythmia(s) treated during the repeat ablation, along with their corresponding targets.
- **Freedom from documented (symptomatic and asymptomatic) atrial tachyarrhythmia off Class I/III AAD:** Defined as freedom from documented (symptomatic and asymptomatic) atrial tachyarrhythmia episodes based on electrocardiographic data (≥ 30 seconds on ECG or sponsor provided CEM or Holter device) during the effectiveness evaluation period (Day 91-Day 365). Taking any Class I/III AAD for AF/AT/AFL of unknown origin beyond the 3-month visit window (i.e., any time from Day 105-365 post index procedure) will also be deemed a failure.
- **12 Month Single Procedure Treatment Success:** Defined as freedom from documented symptomatic atrial tachyarrhythmia episodes based on electrocardiographic data (≥ 30 seconds on ECG or sponsor provided CEM or Holter device) during the effectiveness evaluation period (Day 91-Day 365) following a single index ablation procedure with all other failure modes included.
- **Clinical Success:** Defined as freedom from documented symptomatic atrial tachyarrhythmia episodes based on electrocardiographic data (≥ 30 seconds on ECG or sponsor provided CEM or Holter device) during the effectiveness evaluation period (Day 91-Day 365).
- **Canadian Cardiovascular Society – Severity of Atrial Fibrillation (CCS-SAF):** Defined as improvement in scores of Class 0 to Class 4 at 12 months post procedure compared to baseline.
- **Reduction in Cardiovascular (CV) Hospitalization:** Defined as reduction in CV hospitalization 12 months post procedure (not including repeat procedures) compared to 6 months prior to enrollment.
- **Reduction in DCCV:** Defined as reduction in DCCVs 12 months post procedure compared to 6 months prior to enrollment.
- **AAD Utilization by Timing:** Defined the proportion of subjects on AADs by timing compared to baseline.

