9.2.4.2 Effectiveness Endpoints

The following additional effectiveness endpoints will be assessed:

- Acute procedural success, defined as the percent of subjects with electrical isolation of all PVs with confirmed entrance block at the end of the procedure.
 - Acute reconnection identified by adenosine/isoproterenol challenge.
 - First pass isolation (achievement of entrance block after first encirclement evaluated prior to the 30-min waiting period and adenosine challenge)
 - Ablation by a non-study catheter for PVI (touch-up) among all clinically relevant targeted PVs and by subject
- Repeat ablation procedures
 - Timing (blanking period or after blanking)
 - % PV reconnection by targeted PV and by subject
 - Arrhythmia treated or non-PV targets
- Freedom from documented (symptomatic and asymptomatic) atrial tachyarrhythmia episodes based on electrocardiographic data (≥ 30 seconds on ECG or sponsor provided TTM or Holter device) during the effectiveness evaluation period (Day 91-Day 365) with the following criteria also deemed failure:
 - Taking any AAD (Class I or III) for AF beyond the 3-month follow-up visit window (i.e., at any time from day 105-365 post index procedure).
- 12 Month Single Procedure Treatment Success off AAD: The 12-month single procedure success is defined as freedom from documented symptomatic AF/AT/AFL (of unknown origin⁺) episodes based on electrocardiographic data (≥ 30 seconds on ECG or sponsor provided TTM or Holter device) through the effectiveness evaluation period following a single index ablation procedure with all other failure modes included:
 - Acute procedural failure
 - Non-study catheter failure, including:
 - use of a non-study catheter (NSC) to treat pulmonary vein targets/isolation of clinically relevant PVs (all PVs except those that are silent and/or cannot be cannulated) and left atrial non-PV AF targets during the index procedure.
 - AAD failure: Taking a new AAD (Class I & III) for atrial tachyarrhythmia (AF, AT or AFL of unknown origin⁺) or taking a previously failed Class I/III AAD, at a greater than the highest ineffective historical dose, for AF/AFL/AT beyond the 3-month follow-up visit window (i.e., at any time from day 105-365 post index procedure).

- Any DC cardioversion procedure during the evaluation period for documented atrial tachyarrhythmia (AF, AT or AFL of unknown origin[†]) recurrences ascertained through protocol specified arrhythmia monitoring methods (12-lead ECG, TTM and Holter).

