13.4 Repeat Procedures

Repeat procedures may be performed at the discretion of the investigator. Repeat procedures for AF/AFL of unknown origin⁺/AT recurrences during the blanking period (0-90 days) MUST be performed using the study catheter for ablating PV reconnections. More than 1 repeat procedure for AF/AFL of unknown origin⁺/AT during the blanking period is considered a failure mode for primary effectiveness. Procedures for CTI dependent flutter in the follow up period are not considered repeat procedures per protocol. Repeat procedures for AF/AFL of unknown origin⁺/AT recurrences during the evaluation period (91-365 days) may be managed per investigator discretion using an approved ablation catheter. The follow-up schedule will remain based on the initial ablation procedure.

For the repeat procedures for AF/AFL of unknown origin⁺/AT recurrences, investigators must collect and provide information on location of reconnections of PVs and in case of atrial flutter recurrence, confirm if CTI dependent flutter or AFL of unknown origin.

⁺AFL of unknown origin is defined as all AFL except those CTI dependent AFL as confirmed by 12-Lead ECG and entrainment maneuvers in an EP study.

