8.4.1.2. Primary Effectiveness Endpoint

The primary effectiveness endpoint is freedom from documented (symptomatic and asymptomatic) atrial tachyarrhythmia (atrial fibrillation [AF], atrial tachycardia [AT], or atrial flutter [AFL] of unknown origin⁺) episodes based on electrocardiographic data (≥ 30 seconds on an electrocardiogram [ECG], sponsor-provided cardiac event monitor [CEM], or Holter device) during the effectiveness evaluation period (Day 91-365 post index procedure) and freedom from the following failure modes:

- **Acute procedural failure**, defined as failure to confirm entrance block in all pulmonary veins (except those that are silent and/or cannot be cannulated post-procedure) at the end of the procedure.
- **Repeat ablation failure**, including:
 - More than 1 repeat ablation procedures for AF/AT/AFL of unknown origin⁺ during the 3-Month Blanking Period (Day 0-90 post index procedure).
 - Any repeat ablation procedure for AF/AT/AFL of unknown origin⁺ during the evaluation period.
- **Non-study catheter failure**, including:
 - Use of a NSC to treat pulmonary vein targets to achieve isolation of clinically relevant PVs (all PVs except those that are silent and/or cannot be cannulated) and/or to ablate left atrial non-PV AF targets during the index procedure.
 - Use of a NSC to treat pulmonary vein targets to achieve isolation of clinically relevant PVs (all PVs except those that are silent and/or cannot be cannulated) during repeat procedure in the blanking period.
- **AAD failure**, defined as taking a new Class I/III AAD for atrial tachyarrhythmia (AF, AT or AFL of unknown origin⁺) or taking a previously failed Class I/III AAD at a greater than the highest ineffective historical dose for AF/AT/AFL beyond the 3-month follow-up visit window (i.e., at any time from day 105-365 post index procedure).
- **Continuous AF/AT/AFL of unknown origin⁺** on a standard 12-lead ECG during the effectiveness evaluation period.
- **Any Direct Current Cardioversion (DCCV) procedure** during the evaluation period for documented atrial tachyarrhythmia (AF, AT or AFL of unknown origin⁺) recurrences ascertained through protocol specified arrhythmia monitoring methods (12-lead ECG, CEM and Holter monitor).

⁺AFL of unknown origin is defined as all AFL except those cavotricuspid isthmus (CTI) dependent AFL as confirmed by 12-Lead ECG and entrainment maneuvers in an EP study.

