8.13.2 Additional Effectiveness Endpoints

The additional effectiveness endpoints will be summarized descriptively as described below and will be conducted in the Pilot SA, Pivotal main study mITT and PP, and Pivotal Roll-In analysis sets.

- **Acute procedural success:** The number and percentage of subjects and clinically relevant targeted PVs with acute procedural success will be presented.
- **Acute reconnection:** The number and percentage subjects and clinically relevant targeted PVs where acute reconnection was identified by adenosine/isoproterenol challenge will be presented:

[REDACTED]

[REDACTED]

[REDACTED]

- **FPI:** The number and percentage of subjects and clinically relevant targeted PVs with achievement of entrance block after first encirclement evaluated prior to the adenosine challenge:

■ [REDACTED]
■ [REDACTED]
■ [REDACTED]
■ [REDACTED]

- **Touch-up by NSC:** The number and percentage of subjects and clinically relevant targeted PVs ablated by a NSC to achieve PVI:

■ [REDACTED]
■ [REDACTED]
■ [REDACTED]
■ [REDACTED]

- **Repeat ablation procedure:**

- **Occurrence of repeat procedures:** Kaplan-Meier estimates and plots will be used to characterize the time to the first repeat ablation procedure for AF/AT/AFL of unknown origin. The proportion of subjects who are free from repeat ablation for AF/AT/AFL of unknown origin at each monthly timepoint post index procedure will be presented.

[REDACTED]
[REDACTED]
[REDACTED]
[REDACTED]

- **PV reconnection:** The number and percentage of subjects and PVs and at the repeat procedure where PV reconnection was observed:

■ [REDACTED]

- **Freedom from documented (symptomatic and asymptomatic) atrial tachyarrhythmia off Class I/III AAD:** Kaplan-Meier estimates and plots will be used to characterize the time to first documented (symptomatic and asymptomatic) atrial tachyarrhythmia episodes based on electrocardiographic data (≥ 30 seconds on ECG or sponsor provided CEM or Holter device) during the effectiveness evaluation period (Day 91-Day 365). Taking any Class I/III AAD for AF/AT/AFL of unknown origin during the evaluation period will also be deemed a failure. The proportion of subjects who are free from failure at each monthly time point post blanking will be presented.

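### The off-AAD arrhythmia-freedom endpoint does not fail a Day 91-365 repeat ablation, so subjects re-ablated without a qualifying recording on Day 91-365 stay successes

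*SAP*

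**What the plan says.** **Off-AAD endpoint, arrhythmia limb.** SAP 8.4.3.2: "Defined as freedom from documented (symptomatic and asymptomatic) atrial tachyarrhythmia episodes based on electrocardiographic data", with a threshold of 30 seconds on ECG, sponsor-provided monitor or Holter, over Day 91-365.

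**Off-AAD endpoint, drug limb.** SAP 8.4.3.2 adds that Class I/III AAD use for AF/AT/AFL of unknown origin "beyond the 3-month visit window (i.e., any time from Day 105-365 post index procedure) will also be deemed a failure". Protocol 9.2.4.2 likewise adds one criterion: "Taking any AAD (Class I or III) for AF beyond the 3-month follow-up visit window". The Kaplan-Meier description in SAP 8.13.2 also adds only the drug criterion: "Taking any Class I/III AAD for AF/AT/AFL of unknown origin during the evaluation period will also be deemed a failure". It then says: "The proportion of subjects who are free from failure at each monthly time point post blanking will be presented".

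**Repeat ablation elsewhere.** The primary effectiveness endpoint (SAP 8.4.1.2) lists as a separate failure mode "Any repeat ablation procedure for AF/AT/AFL of unknown origin" in the evaluation period. Protocol 13.4 says that evaluation-period repeat procedures "may be managed per investigator discretion using an approved ablation catheter". SAP 8.13.2 gives repeat ablation its own Kaplan-Meier curve.

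**Clinical Success.** SAP 8.4.3.2: "Defined as freedom from documented symptomatic atrial tachyarrhythmia episodes based on electrocardiographic data", on Day 91-365. Neither drug use nor repeat ablation is listed as a failure.

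**Status.** SAP 8.4.3 and 8.13 make all additional endpoints descriptive, without hypothesis tests.

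**The concern.** A reader will take the off-AAD curve as the 12-month arrhythmia freedom that the study ablation gives without drug support. A subject whose rhythm is held by a Class I/III drug after Day 104 fails. A subject whose rhythm is held by a second ablation in the evaluation period does not fail for that reason. The study system is investigational here, so an approved catheter is a different device.

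No other endpoint does the same job. The primary endpoint tolerates a previously failed AAD up to its highest ineffective historical dose. Single Procedure Treatment Success counts only symptomatic episodes. The off-AAD endpoint is the only one that joins all documented arrhythmia, symptomatic or not, with freedom from any Class I/III AAD taken for the arrhythmia. The separate repeat-ablation curve cannot correct it, because two marginal curves do not show which re-ablated subjects are counted as event-free.

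**Working it through.** The plan states no figure to reproduce on this point. The check has two parts: which subjects escape, and how large the effect could be.

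**Step 1. Which subjects escape**

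| Subject | Off-AAD endpoint | Clinical Success | Primary endpoint |
|---|---|---|---|
| Asymptomatic recording of at least 30 s on Day 91-365, then re-ablated in that period | Failure | Success, if no symptomatic recording | Failure |
| Symptomatic recording of at least 30 s on Day 91-365, then re-ablated in that period | Failure | Failure | Failure |
| Recurrence documented only in blanking, re-ablated on Day 91-365, no qualifying recording on Day 91-365, no Class I/III AAD in the failure window | **Success** | **Success** | Failure |

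Only the third row is a gap in the off-AAD endpoint. An example is AF recorded on Day 70, re-ablation on Day 100 and no qualifying recording from Day 91 to Day 365.

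**Step 2. Can the third row occur?** Protocol 13.8 requires weekly transmissions from Day 91 to the end of month 5, then monthly ones, with symptom-triggered transmissions and 24-hour Holters at 6 and 12 months. This coverage is regular but intermittent, so paroxysmal episodes can be missed. The structure of the primary endpoint points the same way. Its cardioversion mode is tied to recurrences found by protocol-specified monitoring, whereas its repeat-ablation mode carries no such condition. That mode therefore catches subjects whom the recordings miss.

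**Step 3. Size.** Let

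- f = share of subjects with a repeat ablation for AF/AT/AFL of unknown origin on Day 91-365;
- u = share of those with no qualifying recording on Day 91-365.

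Making such re-ablations failures lowers the success proportion by f x u. The documents give neither value, so both are assumed. Change in percentage points:

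| f | u = 0 | u = 10% | u = 25% | u = 50% | u = 100% (ceiling) |
|---|---|---|---|---|---|
| 3% | 0 | 0.3 | 0.75 | 1.5 | 3 |
| 5% | 0 | 0.5 | 1.25 | 2.5 | 5 |
| 10% | 0 | 1.0 | 2.5 | 5.0 | 10 |
| 15% | 0 | 1.5 | 3.75 | 7.5 | 15 |

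Over f = 3-15% and u = 10-50%:

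- low: 0.03 x 0.10 = 0.003, or 0.3 points; 0.003 x 225 = 0.7 subjects;
- high: 0.15 x 0.50 = 0.075, or 7.5 points; 0.075 x 225 = 16.9 subjects.

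The 225 is the planned evaluable main-phase number. The analysis-set definitions are redacted, so the actual denominators may differ. A re-ablated subject without a recording who also takes a Class I/III AAD for the arrhythmia in the failure window fails already, so f x u slightly overstates the change.

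**The case against.** The strongest case on the other side has five parts.

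1. **The arrhythmia limb does most of the work.** A reader might infer that rhythm control from a second ablation generally counts as success. The documents do not support that. Any qualifying recording on Day 91-365, before or after the re-ablation, is a failure that the second procedure cannot undo. This objection stands and limits the point to re-ablations without such a recording.

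2. **The drug clause gives effect to the endpoint's name.** It covers any Class I/III AAD taken for the arrhythmia, and cardioversion is not listed either, so this need not be a rescue composite with a part left out. That is a fair reading of intent. It does not tell the reader of the curve that repeat procedures are allowed.

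3. **Clinical Success.** A reader might infer the same imbalance there. It does not exist, because that endpoint ignores drug and ablation alike. It is more exposed to re-ablation, since an asymptomatic recording does not fail the subject, but it is consistent as a measure of symptomatic recurrence.

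4. **Other endpoints and the lack of inferential weight.** The primary endpoint fails evaluation-period repeat ablation, one additional endpoint is restricted to a single procedure, and repeat ablation is reported separately. A reader might infer that study success is at risk. It is not: SAP 8.5.3 rests success on the two primary endpoints alone.

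5. **Redaction and evidence of size.** General Conventions and the Kaplan-Meier sensitivity text in the SAP are blacked out and could hold a censoring rule, so its absence can be stated only for the visible text. A large share without recordings is also unsupported, given weekly transmissions from Day 91. Recurrence seen only on telemetry or an implanted recorder is a debatable route, because protocol Appendix III accepts both as documentation although the endpoint names only ECG, sponsor-provided monitor and Holter. All of this stands as a limit on size and certainty.

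**Conclusion.** The point holds in a limited form. In the visible text, the off-AAD endpoint keeps as successes those subjects who are re-ablated on Day 91-365, have no qualifying recording in that period and take no Class I/III AAD for the arrhythmia in the failure window. They remain event-free partly because of a second procedure, possibly with another device. The effect on the reported rate has one direction: upwards.

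Its size is f x u: nil if every re-ablated subject has a qualifying recording, and 0.3-7.5 points over the assumed ranges. Those ranges show scale and are not estimates from the documents. The figure is the change from reclassifying these subjects. It is not the causal effect of the second ablation, because some might have stayed arrhythmia-free without it.

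This is a worthwhile, cheap improvement to a descriptive endpoint. It does not touch the primary or secondary hypotheses.

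**What to change.** **Off-AAD endpoint.** In protocol 9.2.4.2 and SAP 8.4.3.2 and 8.13.2, state that any repeat ablation for AF/AT/AFL of unknown origin on Day 91-365 is a failure, dated to the day of the procedure. Procedures for CTI-dependent flutter stay outside, as in protocol 13.4. At minimum, report that version beside the current one and label the current one as allowing repeat procedures.

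**Clinical Success.** Keep the definition, and add a labelled supplementary version with repeat ablation as failure.

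**Blanking period.** Do not carry over the primary endpoint's rule on more than one repeat ablation in blanking. The argument here does not support it, and it would date failures before Day 91 on curves reported after blanking.

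**Related wording.** If a redacted section already censors at repeat ablation, cite it in SAP 8.13.2. Censoring would still treat ablation differently from drug use, which is a failure. In the same edit, reconcile the AAD failure window: Day 105-365 in SAP 8.4.3.2, but the evaluation period (Day 91-365) in 8.13.2.

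**Cost.** Wording in two documents and one extra derivation. Protocol 13.5 already has ablations after the index procedure recorded. The descriptive rate may fall slightly; the primary endpoints, power and study success do not change.

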- Clinical Success: defined as freedom from documented symptomatic atrial tachyarrhythmia episodes based on electrocardiographic data (≥ 30 seconds on ECG or sponsor provided TTM or Holter device) during the effectiveness evaluation period (Day 91-Day 365)
- QOL Improvement: Canadian Cardiovascular Society – Severity of Atrial Fibrillation (CCS-SAF): defined as improvement in scores of Class 0 to Class 4 at 12M post procedure compared to baseline scores of Class 0 to Class 4.
- Reduction in Cardiovascular hospitalization rates: defined as reduction in CV hospitalization 6M prior to enrollment compared to 12M post procedure
- Reduction in DC Cardioversion defined as number of DCCV 6M prior to enrollment compared to 12M post procedure
- AAD Utilization by timing: Defined as proportion of subjects on antiarrhythmic drugs by timing compared to baseline

[†]AFL of unknown origin is defined as all AFL except those CTI dependent AFL as confirmed by 12-Lead electrocardiogram (ECG) and entrainment maneuvers in an EP study

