9.3 Healthcare Utilization Data

Health care utilization pre-, during and post-hospitalization for the study index ablation procedure, as well as any additional hospitalizations during the study period will be collected. Because this data does not support the safety and efficacy of the VARIPULSE catheter, it will not be provided to the FDA as part of the IDE reporting.

In addition, the sponsor will also collect data associated with follow up care, including any repeat ablation procedure for treating arrhythmia, any inpatient or outpatient visit (including ER admissions, outpatient visits) to address post-procedural complications, any procedure related condition, or any arrhythmia or cardiovascular related conditions.

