10.2 Eligibility Criteria

Inclusion Criteria

Candidates for this study must meet ALL of the following criteria:

1. Symptomatic paroxysmal AF with:
 - a. At least two (2) symptomatic AF episodes within last six (6) months from enrollment
 - b. At least one (1) AF episode electrocardiographically documented within 12 months prior to enrollment. Electrocardiographic documentation may include, but is not limited to electrocardiogram (ECG); Transtelephonic monitoring (TTM), Holter monitor or telemetry strip, and
 - c. A physician's note indicating recurrent self-terminating AF within 7 days.
2. Failed at least one (1) AAD (Class I or Class III) as evidenced by recurrent symptomatic AF, intolerable side effects to the AAD, or contraindication to the AAD
3. Age 18-75 years
4. Willing and capable of providing consent
5. Able and willing to comply with all pre-, post- and follow-up testing and requirements.

Exclusion Criteria

Subjects will be excluded from the study if they meet ANY of the following criteria.

1. Previously diagnosed with persistent AF (> 7 days in duration)
2. AF secondary to electrolyte imbalance, thyroid disease, or reversible or non-cardiac cause (e.g., untreated documented obstructive sleep apnea and acute alcohol toxicity).
3. Previous surgical or catheter ablation for AF
4. Patients known to require ablation outside the PV ostia and outside the CTI region (e.g., atrioventricular reentrant tachycardia, atrioventricular nodal reentry tachycardia, atrial tachycardia, ventricular tachycardia and Wolff-Parkinson White)
5. Documented severe dilatation of the LA (LAD >50mm) antero-posterior diameter on imaging within 6 months prior to enrollment.
6. Documented LA thrombus by imaging within 48 hours of the procedure.

7. Documented severely compromised LVEF (LVEF <40%) by imaging within 6 months prior to enrollment
8. Uncontrolled heart failure or New York Heart Association (NYHA) Class III or IV
9. History of blood clotting, bleeding abnormalities or contraindication to anticoagulation (heparin, warfarin, or dabigatran),
10. Documented thromboembolic event (including TIA) within the past 12 months
11. Previous PCI/MI within the past 2 months
12. Coronary Artery Bypass Grafting (CABG) surgery within the past 6 months (180 days)
13. Valvular cardiac surgical/percutaneous procedure (i.e., ventriculotomy, atriotomy, valve repair or replacement and presence of a prosthetic valve).
14. Unstable angina within 6 months

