8.13 Additional Endpoint Analyses

No formal statistical hypotheses will be formulated or performed for the additional endpoints. Descriptive statistics will be provided on all additional endpoints in the analysis sets specified below.

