- **12 Month Single Procedure Treatment Success:** Kaplan-Meier estimates and plots will be used to characterize the time to first documented symptomatic atrial tachyarrhythmia episodes based on electrocardiographic data (≥ 30 seconds on ECG or sponsor provided CEM or Holter device) during the effectiveness evaluation period (Day 91-Day 365) following a single index ablation procedure with all other failure modes included. The proportion of subjects who are free from failure at each monthly time point post blanking will be presented.
- **Clinical Success:** Kaplan-Meier estimates and plots will be used to characterize the time to first documented symptomatic atrial tachyarrhythmia episodes based on electrocardiographic data (≥ 30 seconds on ECG or sponsor provided CEM or Holter device) during the effectiveness evaluation period (Day 91-Day 365). The proportion of subjects who are free from failure at each monthly time point post blanking will be presented.
- **CCS-SAF:** Baseline CCS-SAF scores and the mean change from baseline at each follow-up timepoint the questionnaire is administered will be summarized descriptively. [REDACTED]
[REDACTED]
[REDACTED]
- **Reduction in CV Hospitalization:** Baseline and follow-up rates for the time intervals 0-6 months and >6-12 months will be summarized descriptively. [REDACTED]
[REDACTED]

- **Reduction in DCCV:** Baseline and follow-up rates for the time intervals 0-6 months and >6-12 months will be summarized descriptively. [REDACTED]
- **AAD Utilization by Timing:** Baseline and follow-up AAD usage will be summarized descriptively. [REDACTED]
[REDACTED]
[REDACTED]
[REDACTED]
[REDACTED]
[REDACTED]
[REDACTED] Separate summaries will be presented for all AADs and Class I/III AADs.

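### The SAP leaves repeat procedures out of the follow-up side only of the CV hospitalization comparison, which can enlarge but never shrink the reported reduction

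*SAP*

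**What the plan says.** Protocol 9.2.4.2 lists a reduction in cardiovascular hospitalization rates among the additional effectiveness endpoints, "defined as reduction in CV hospitalization 6M prior to enrollment compared to 12M post procedure". The wording carries no qualifier. It does not mention repeat procedures in either direction.

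SAP 8.4.3.2 restates the endpoint as "reduction in CV hospitalization 12 months post procedure (not including repeat procedures) compared to 6 months prior to enrollment". The parenthesis applies to the post-procedure period only. The next endpoint in the same list, reduction in DC cardioversion, has the same before/after form and removes nothing.

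SAP 8.13.2 gives the analysis: "Baseline and follow-up rates for the time intervals 0-6 months and >6-12 months will be summarized descriptively". Redacted text follows that sentence. SAP 8.13 says of this group of endpoints that "No formal statistical hypotheses will be formulated or performed for the additional endpoints".

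Three other provisions matter here:

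- Protocol 10.2 excludes patients with "Previous surgical or catheter ablation for AF".
- Protocol 9.3 collects data on care during follow-up, "including any repeat ablation procedure for treating arrhythmia".
- SAP 8.13.2 reports repeat ablation on its own: "Kaplan-Meier estimates and plots will be used to characterize the time to the first repeat ablation procedure for AF/AT/AFL of unknown origin".

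**The concern.** A before/after comparison is fair only if the same kinds of event count on both sides. Here one kind of admission is taken out of follow-up. Because of the eligibility rule, that kind cannot occur at baseline as an AF ablation. The split into two 6-month intervals in SAP 8.13.2 makes the periods equal in length, but it does not touch this asymmetry.

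The admissions removed are those for redoing the ablation after recurrence. Other parts of the plan do not fully put them back:

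- Under Protocol 14.1, re-ablation for AF and the hospital stay that goes with it are not in themselves an adverse event, so these stays do not appear as SAEs.
- In the primary effectiveness endpoint, the repeat-ablation failure mode for the blanking period needs "More than 1 repeat ablation procedures for AF/AT/AFL of unknown origin". A single blanking-period repeat is thus not a failure on that criterion, and under the SAP it is not a CV hospitalization either.

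What is at stake is how a descriptive result is read. A stated percentage reduction in CV hospitalization would rest on a narrower count than the protocol's wording suggests, and the visible text gives no reason for the change.

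**Working it through.** The visible text gives no hospitalization rate, repeat rate or expected reduction for this endpoint, so there is no stated figure to reproduce. The direction follows from the definitions. The size needs assumed rates.

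**Inputs from the documents**

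- Removal on the follow-up side only: SAP 8.4.3.2.
- No removal on either side: Protocol 9.2.4.2.
- No prior AF ablation in enrolled subjects: Protocol 10.2, exclusion criterion 3.
- Follow-up rates by 6-month interval: SAP 8.13.2.

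**Inputs assumed**

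- b = baseline CV hospitalizations per subject per 6 months: 0.10, 0.20, 0.30.
- R = repeat-procedure admissions per subject over 12 months: 0.02, 0.05, 0.10. Split evenly, each 6-month interval has r = R/2. In 225 evaluable subjects, R runs from 225 × 0.02 = 4.5 to 225 × 0.10 = 22.5 admissions.
- f = all other follow-up CV hospitalizations per subject per 6 months, set at b/2 to give the table a starting level. The difference does not depend on f.

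**Formulas, per 6-month interval**

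- Reduction under the SAP definition: 1 − f/b.
- Reduction with repeat-procedure admissions counted: 1 − (f + r)/b.
- Difference: (1 − f/b) − (1 − (f + r)/b) = r/b, which is never negative.

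**Example.** Take b = 0.20 and R = 0.05, so r = 0.025 and f = 0.10. The SAP reduction is 1 − 0.10/0.20 = 50%. With repeats counted it is 1 − 0.125/0.20 = 37.5%. The difference is 0.025/0.20 = 12.5 points.

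**Full range.** The SAP reduction is 50% in every row, because f = b/2.

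| b | R | r = R/2 | Reduction with repeats counted | Difference r/b (points) |
|---|---|---|---|---|
| 0.10 | 0.02 | 0.010 | 40.0% | 10.0 |
| 0.10 | 0.05 | 0.025 | 25.0% | 25.0 |
| 0.10 | 0.10 | 0.050 | 0% | 50.0 |
| 0.20 | 0.02 | 0.010 | 45.0% | 5.0 |
| 0.20 | 0.05 | 0.025 | 37.5% | 12.5 |
| 0.20 | 0.10 | 0.050 | 25.0% | 25.0 |
| 0.30 | 0.02 | 0.010 | 46.7% | 3.3 |
| 0.30 | 0.05 | 0.025 | 41.7% | 8.3 |
| 0.30 | 0.10 | 0.050 | 33.3% | 16.7 |

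**Variations**

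- All repeat admissions in one interval: r = R there. The difference in that interval runs from 0.02/0.30 = 6.7 points to 0.10/0.10 = 100 points, and it is zero in the other interval.
- No repeat procedure leads to a counted admission: r = 0 and the two definitions agree. This is possible. The only visible meaning of hospitalization, given for SAEs in Protocol 14.2.2, involves at least an overnight stay, so same-day repeats might not count.
- Summary as percent of subjects hospitalized: the difference is at most r/b, because a subject with another CV admission is already counted.

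**The case against.** The case for leaving the SAP as it stands has several parts.

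**The protocol is silent, not contrary.** A reader might infer that the SAP breaks an explicit protocol rule to count repeat-procedure admissions. The text does not support that. Protocol 9.2.4.2 is unqualified, the visible text does not define CV hospitalization, and Protocol section 18 leaves the description of planned analyses to the SAP. The exclusion can be read as an openly stated clarification. It also has some footing in Protocol 14.1, which captures re-ablation separately from adverse events, although that rule concerns event reporting and not this endpoint. What remains is that the two definitions differ, and the change can move the result in one direction only.

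**Most admissions for recurrence still count.** A reader might infer that the SAP strips out every admission due to treatment failure. It does not. Only repeat procedures are named, so admissions for recurrent AF, for cardioversion or for other CV causes stay in. The baseline side is not wholly free of ablation admissions either: criterion 3 bars prior ablation for AF, and by itself it does not bar an earlier flutter ablation.

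**Repeat ablations are visible elsewhere.** They have their own endpoint with timing and Kaplan-Meier estimates, and any repeat for AF/AT/AFL of unknown origin in the evaluation period is a primary effectiveness failure. This stands in part. Those summaries count procedures, or time to the first one, and not admissions, so the hospitalization rate with repeats counted cannot be rebuilt from them.

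**Redaction.** The text after the analysis sentence in SAP 8.13.2 is hidden and might add a version with repeats counted. That cannot be ruled out. The definition in 8.4.3.2 is fully visible and is one-sided.

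**Another parse.** The parenthesis could be meant only to say that the 12 months run from the index procedure. SAP section 4 already fixes that for all intervals, and the DC cardioversion endpoint carries no such note, so exclusion of repeat procedures is the more natural reading.

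**Conclusion.** The point holds in a limited form. The SAP removes repeat procedures from follow-up only, the protocol states the endpoint without that removal, and the eligibility criteria leave no AF-ablation admissions at baseline to balance it. The reported reduction can therefore be larger than, or equal to, the one with repeats counted, but never smaller.

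The size is r/b. At b = 0.10 to 0.30 per subject per 6 months, with 2 to 10 repeat-procedure admissions per 100 subjects over 12 months split evenly, that is 3.3 to 50 percentage points. Both rates are assumptions, and the lower limit is zero. A reader might take any one of these figures as the bias in this trial. The documents do not support that, because they give neither rate.

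A reader might also infer a threat to the trial's conclusions. There is none: the endpoint is additional and has no hypothesis test, and study success under SAP 8.5.3 depends on the two primary endpoints alone. This is a minor correction to a descriptive summary.

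**What to change.** In SAP 8.4.3.2 and 8.13.2, report the follow-up CV hospitalization rate with repeat-procedure admissions counted, which matches the protocol's unqualified wording. Show the rate without them as a second line, labelled as such, and state the reason for that version. If the redacted part of 8.13.2 already provides both, bringing the definition in 8.4.3.2 into line is enough.

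No new data are needed: Protocol 9.3 and 13.5 already collect hospitalizations and repeat ablations during follow-up. The cost is one more summary line and a possibly smaller headline reduction.
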